4. STUDY COHORT

4.1. Number of subjects/centres

This will be a multi-centre study.

There will be five study groups, three of which will receive an investigational NTHi-Mcat vaccine formulation and two placebo groups. The target is to enrol approximately 30 eligible subjects 18–40 years old in Step 1 (~15/group) and approximately 90 eligible subjects 50–70 years old in Step 2 (~30/group). The total target number of subjects is approximately 120 (see also [Table 1](#)).

Please refer to Section [10.3](#) for a detailed description of the criteria used in the determination of sample size.

Approximately 50% of the subjects in each group of Step 2 will be part of a **sub-cohort for CMI analysis**. *Subjects will be selected based on the enrolment order, i.e. the first 50% of the participants (approximately the first 15 subjects/group) will be enrolled in the sub-cohort for CMI*. An additional blood sample for CMI analysis will be taken from those subjects at each of the CMI blood sampling time points (i.e. Day 0, Day 60, Day 90, Day 210 and Day 420). **(Amended 16 March 2016)**

Table 4 Sub-cohorts for CMI

| Sub-cohort name | Description | Estimated number of subjects in Step 2 |
|-----------------|--|--|
| CMI | An additional blood sample will be taken from about 50% of subjects in each group of Step 2 for CMI analysis | ~15/ group ~45 in total |

CMI: cell-mediated immunity

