5.2.2.2.1. Study group and treatment number allocation

The target will be to enrol approximately 120 eligible subjects who will be randomly assigned per step:

- **Step 1:** two study groups in a (1:1) ratio (approximately 15 subjects per group).
- **Step 2:** three study groups in a (1:1:1) ratio (approximately 30 subjects per group).

Allocation of the subject to a study group at the investigator site will be performed using SBIR.

Subjects will be minimised for centre at Step 1. At Step 2, subjects will be minimised for age (50-59 years or 60-70 years), for smoking status (current or former smokers), for centre and for forced expiratory volume in 1 second (FEV₁) / forced vital capacity (FVC) (≥ 0.7 or < 0.7). Minimisation factors will have equal weight in the minimisation algorithm.

As several minimisation factors have been defined for the treatment allocation at Step 2, it was decided at the design phase not to minimise for the CMI group allocation. This wouldn't be feasible from an implementation point of view. (Amended 16 March 2016)

After obtaining the signed and dated ICF from the subject (at Screening Visit) and after having checked the eligibility of the subject, the dedicated study staff will access SBIR (at Visit 1). Upon providing the information for each minimisation factor and the subject identification number, the randomisation system will determine the study group and will provide the treatment number to be used for the first dose. This treatment number will be used by the dedicated staff member for administration of the vaccine.

The number of each administered treatment must be recorded in the eCRF on the Vaccine Administration screen.

When SBIR is not available, please refer to the SBIR user guide or the Study Procedures Manual (SPM) for specific instructions.

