7.1.3.1. Humoral immune response

Within group evaluation

For each group, at each time point during which blood samples are collected for humoral immune response and for each assay:

- Seropositivity rate and their exact 95% CI will be tabulated.
- GMCs and their 95% CI will be calculated.
- Antibody concentrations distribution will be investigated using Reverse Cumulative Curves.

These analyses will also be performed for each level of the following minimisation factors: age (50-59 years vs. 60-70 years), smoking status (current vs. former smoker), FEV₁/FCV ratio (≥ 0.7 vs. < 0.7).

Between groups evaluation (only for Step 2)

Comparative analyses will be exploratory with the aim to characterise the difference between the 10-10-10-AS and 10-10-3-AS groups in humoral immune response.

The difference in terms of GMCs will be evaluated, one month post-Dose 2, by computing the 95% CIs of the GMC ratio between groups for Step 2 by using a one-way ANCOVA model on the logarithm10 transformation of the concentrations/ titres. The ANCOVA model will include the group category, the age category, the smoking status and FEV₁/FVC (≥ 0.7 or < 0.7) and the pre-Dose 1 concentration (as covariate) as fixed effects. The groups will be considered significantly different if the 95% CI for the GMC ratio between the two groups does not contain the value 1.

However, these differences should be interpreted with caution considering that there will be no adjustment for multiplicity of endpoints.

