8. STATISTICAL CALCULATIONS

The study groups will be defined by treatment actually administered at Dose 1.

Demography

- For a given subject and a given demographic variable, missing measurement will not be replaced.
- Age: Age at the reference activity, computed as the number of units between the date of birth and the reference activity In case of partial dates of any of these 2 dates:
 - 15th of month, If only the day is missing
 - 30th of June, if day and months are missing

Immunogenicity

- For a given subject and the analysis of a given immunogenicity measurement, missing or un-evaluatable measurements will not be replaced.
- A seronegative subject is defined as a subject whose antibody concentration is below the assay cut-off value.
- A seropositive subject is defined as a subject whose antibody concentration is greater than or equal to the assay cut-off value.
- Antibody concentrations below the assay cut-off will be given an arbitrary value of half the assay cut-off for the purpose of geometric mean concentration (GMC) calculation.
- Calculation of the GMCs will be performed by taking the anti-logarithm in base 10 (anti-log10) of the mean of the log10 concentration/titre transformations.
- All confidence intervals (CIs) computed will be two-sided 95% CIs.
- The assay cut-off is the value under which there is no quantifiable result available. For an assay with a specific 'cut_off' , numerical immuno result is derived from a character field (rawres):
 - If rawres is 'NEG' or '-' or '(-)', numeric result= cutt_off/2,
 - if rawres is 'POS' or '+' or '(+)', numeric result = cut_off,
 - if rawres is '< value' and value<=cut_off, numeric result =cut_off/2,
 - if rawres is '< value' and value>cut_off, numeric result =value,
 - if rawres is '> value' and value<cut_off, numeric result =cut_off/2,
 - if rawres is '> value' and value>=cut_off, numeric result =value,
 - if rawres is '<= value' or '>= value' and value<cut_off, numeric result =cut_off/2,
 - if rawres is '<= value' or '>= value' and value>=cut_off, numeric result =value,
 - if rawres is a value < cut_off, numeric result = cut_off/2,

Statistical Analysis Plan

Study alias & e-track number(s): NTHI MCAT-001 (201281)

- if rawres is a value \geq cut_off, numeric result = rawres,
- else numeric result is left blank.

Safety/reactogenicity

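### The Step 2 ANCOVA adjusts for three of the four minimisation factors and omits centre without giving a reason; if centre is prognostic, the GMC-ratio intervals are conservative

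*SAP*

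**What the plan says.** Protocol 5.2.2.2.1 sets the allocation: "At Step 2, subjects will be minimised for age (50-59 years or 60-70 years), for smoking status (current or former smokers), for centre", and finally for FEV1/FVC. It adds: "Minimisation factors will have equal weight in the minimisation algorithm". Step 2 randomises to "three study groups in a (1:1:1) ratio (approximately 30 subjects per group").

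SAP Amendment 2, 7.1.3.1, sets the model for the GMC ratio one month after Dose 2: "The ANCOVA model will include the group category, the age category, the smoking status", FEV1/FVC, "and the pre-Dose 1 concentration (as covariate) as fixed effects". SAP 7.2.3.1 and protocol 10.6.3.1 list the same terms. Centre appears in none of the three, and no reason is given. The subgroup analyses by minimisation factor in the same sections also leave centre out.

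On centres, protocol 4.1 says only: "This will be a multi-centre study". SAP section 8 sets the interval: "All confidence intervals (CIs) computed will be two-sided 95% CIs".

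**The concern.** Minimising on centre makes the groups similar within centre, so differences between centres largely cancel from the group comparison. A model without centre does not credit this. It leaves the between-centre variation in the residual, and the reported standard error is then larger than the true sampling error of the estimate. The plan evidently means to adjust for its allocation factors, since it does so for the other three.

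What is at stake is a missed difference, not a false one. Two adjuvanted groups of about 30 are called significantly different when the interval excludes 1. SAP 7.2.3.3 then expects significance on at least one GMC to confirm the selected group for future studies.

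**Working it through.** **The plan's own figure.** The only numerical sample-size figure for Step 2 (protocol 10.3) is the chance of seeing an adverse event of 5% incidence in 30 subjects: 1 - 0.95^30 = 0.785, the stated 78.5%. It reproduces but does not bear on the ANCOVA. The documents give no SD, power or target width for the GMC ratio.

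**Inputs from the documents.** About 30 per group; two-sided 95% intervals; model terms as listed above. The documents do not say whether placebo subjects enter the model, so both cases are shown.
- Two active groups: N = 60, six parameters (intercept, group, age, smoking, FEV1/FVC, baseline), residual df = 60 - 6 = 54.
- All three groups: N = 90, seven parameters, residual df = 90 - 7 = 83.

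**Assumed inputs.** Number of centres k: 2 to 10. Share r of residual log10 variance due to centre, after the listed covariates: 0, 5%, 10%, 20%.

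**Formula.** With centre balanced across groups, the ratio of interval widths on the log10 scale, without centre to with centre, is

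[t(0.975, df) / t(0.975, df - (k - 1))] / sqrt(1 - r).

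Example with N = 60, k = 4, r = 0.10: (2.0049 / 2.0076) / sqrt(0.90) = 1.0527, so omitting centre makes the interval about 5% wider.

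**Simulation check.** The formula assumes exact balance. Step 2 was therefore simulated with minimisation on four equally weighted factors. The assumptions were a 0.8 probability of the best-balancing group, equally likely centres, and about 1,200 trials per setting. Entries are width without centre divided by width with centre.

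| r | Formula, N = 60, k = 2 to 10 | Simulated, two active groups, k = 2 / 4 / 8 | Simulated, all three groups, k = 2 / 4 / 8 |
|---|---|---|---|
| 0 | 0.9996 to 0.9954 | 0.999 / 0.993 / 0.972 | 1.000 / 0.996 / 0.984 |
| 5% | 1.026 to 1.021 | 1.025 / 1.021 / 0.999 | 1.025 / 1.023 / 1.008 |
| 10% | 1.054 to 1.049 | 1.055 / 1.049 / 1.027 | 1.057 / 1.052 / 1.039 |
| 20% | 1.118 to 1.113 | 1.124 / 1.115 / 1.089 | 1.121 / 1.116 / 1.098 |

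The formula with N = 90 gives nearly the same values (r = 10%: 1.054 to 1.052).

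**Reading the table.**
- With a real centre effect, omission widens the interval by about 0-3% (r = 5%), 3-6% (10%) or 9-12% (20%).
- With no centre effect the sign reverses. Including centre costs up to 1/0.9954 - 1 = 0.5% by the formula, and 1/0.972 - 1 = 2.9% in the worst simulated case. That case has 8 centres among 60 subjects, or 60/8 = 7.5 subjects per centre.
- At r = 10%, ignoring degrees of freedom, the planned model on 30 per group reports the width that a model with centre would give on about 30 x 0.90 = 27 per group.

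**Coverage.** At r = 20%, simulated coverage without centre was 96.1% to 97.6% against a nominal 95%. The simulation standard error is about sqrt(0.95 x 0.05 / 1200) = 0.6 percentage points, so the lower end is not clearly above nominal and the upper end is. The direction is conservative.

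**The case against.** The strongest reply is that harm has not been shown. Omission widens the interval only if centre still matters after age, smoking status, lung function and baseline antibody. The ELISAs are run at the sponsor's or a designated laboratory under standardised procedures (protocol 5.7.3), which removes one obvious source of centre differences. With no centre effect, the planned model is as good or slightly better. Adding centre also costs more than degrees of freedom, because minimisation does not make centre exactly orthogonal to group. With 8 centres the gain at a 5% share disappears. All of this stands, and it is why the effect is stated conditionally.

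It also stands that the comparison is exploratory, that power and type I error are not controlled (protocol 10.7), and that any error is conservative.

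A reader might infer that the interval drives the formulation choice. The documents do not support that. The ranking uses the summary score, which is built from group GMCs and CMI geometric means with a 0.02 threshold, and safety and CMI profile are then reviewed. The ANCOVA interval is not an input. Its only decision role is the confirmatory expectation in SAP 7.2.3.3.

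What the reply does not answer is why three allocation factors are in the model and the fourth is not.

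**Conclusion.** The omission is real, unexplained and consistent across protocol and SAP, so it is an analysis choice to justify or change and not a contradiction between documents. If centre is prognostic for log10 concentration, the GMC-ratio intervals are conservative by the amounts in the working. If it is not, leaving it out does no harm. The size rests on assumed values for the number of centres and the centre variance, and on equally sized centres in the simulation.

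Two stronger readings are tempting. One is that the intervals are simply too wide; this is not established, because the centre variance is unknown and the sign reverses when it is zero. The other is that they are wider than the design allows; the design sets no width, SD or power for this comparison, so there is nothing to exceed. Nor is there evidence of bias or of extra false positives. The point is worth acting on because the change is cheap, but its weight is modest.

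**What to change.** Add centre to the ANCOVA in protocol 10.6.3.1 and SAP 7.1.3.1 and 7.2.3.1 as a fixed factor. Pool small centres by a written rule based on centre size alone, fixed before the statistician is unblinded at the Day 90 analysis (protocol 10.8.1, SAP 9.1). Pooling limits the loss seen with many small centres. A random intercept is less attractive if there are only a few centres, since its variance would be poorly estimated. State in the same place whether placebo subjects enter the model.

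The cost is one model term and a few degrees of freedom. No new data are needed: centre is entered at allocation, and enrolment by site and group is already tabulated (SAP 7.1.1). If the sponsor prefers to keep the present model, the minimum is a stated reason and a pre-specified sensitivity analysis with centre included.

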7.1.3.2. CMI response

The frequency of specific CD4⁺/ CD8⁺ T-cells will be summarised (mean, SD, minimum, Q1, median, Q3, and maximum) by group, at each time point during which blood samples are collected for CMI (descriptive statistics).

Each data will be obtained by subtracting the summary of the background value to each summary value. Values less than or equal to zero will be set to 1 for the purpose of geometric mean calculation and graphical representation.

Study alias & e-track number(s): NTHI MCAT-001 (201281)

7.1.3.3. Summary score to support dose selection

The calculation of a summary score for both active groups of Step 2 (i.e. 10-10-10-AS and 10-10-3-AS) will be proposed in order to help the formulation selection. The group with the highest summary score should potentially be the one considered for selection provided it has an acceptable safety and CMI profile. However note that a difference of less than 0.02 between 2 summary scores will not be sufficient to consider that a formulation should be ranked higher than/prefereed to the other. Unacceptable safety profile encompasses cases such as high occurrence of grade 3 events, occurrence of specific serious adverse event. Unacceptable CMI profile encompasses cases with a pronounced Th₂ response in which there is an isolated elevated IL-13 response, in particular without a response in terms of IFN- γ . The discarding of a group from the selection because of specific safety or CMI reason will be substantiated in the CSR.

If the group(s) ultimately selected for use in upcoming studies for COPD patients is(/are) not the one with the highest summary scores at post dose 2 and/or post dose 3, the disqualification of the group(s) with higher summary scores should be adequately justified in the CSR.

The summary scores will be calculated based on the subjects from the ATP cohort.

For each group g , the summary score will summarize how well the group is performing compared to the average active group in terms of the following immunogenicity and CMI results. Before defining the summary score several quantities are introduced (for XX being PD, PE, PiLA, or *Usp42*):

- GM_{XXg} : the 30 days post last vaccination GMC of Anti- XX of group g
- $AvGM_{XX}$: the 30 days post last vaccination GMC of Anti- XX of all subjects in any active group
- GM_{CMIXXg} : the 30 days post last vaccination GMC of specific Anti- XX CD4+ T cells expressing at least two markers among CD40L, IL-2, TNF-Alpha, IFN-Gamma, IL-13 and IL-17 per million cells of group g
- $AvGM_{CMIXX}$ the 30 days post last vaccination GMC of specific Anti- XX CD4+ T cells expressing at least two markers among CD40L, IL-2, TNF-Alpha, IFN-Gamma, IL-13 and IL-17 per million cells of all subjects in any active group

These measures will be transformed in order to be contained between 0 and 1 via the following formulae:

$$D_{XXg} = 1 / (1 + \text{Exp}((AvGM_{XX} - GM_{XXg})/AvGM_{XX}))$$

$$D_{CMIXXg} = 1 / (1 + \text{Exp}((AvGM_{CMIXX} - GM_{CMIXXg})/AvGM_{CMIXX}))$$

Statistical Analysis Plan

Study alias & e-track number(s): NTHI MCAT-001 (201281)

The following groups will be evaluated at Post-dose 2:

- 10-10-10-AS summary score Post-dose 2
- 10-10-3-AS summary score Post-dose 2

The average GMCs used to calculate the summary scores will be an average of all vaccinated subjects from an active group at post dose 2.

The summary score for group g will be computed by taking the weighted geometric mean of the several D measures as follows:

$$D_g = \sqrt[20]{D_{PDg}^4 \times D_{PEg}^4 \times D_{PilAg}^4 \times D_{UspA2g}^4 \times D_{CMIPDg}^1 \times D_{CMIPEg}^1 \times D_{CMIPilAg}^1 \times D_{CMIUspA2g}^1}$$

A group with a D score of $\frac{1}{2}$ corresponds exactly at the average level of all subjects in the active groups. The highest the value of the summary score for a group, the better the group is performing in terms of immunogenicity and CMI compared to the others.

Differences of less than 0.02 in terms of summary measures will not be considered sufficient to establish a clear hierarchy between 2 groups.

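### The antibody terms of the summary score ignore baseline although an ANCOVA for the same comparison adjusts for it; using adjusted GMCs costs little, and the gain depends on an unstated baseline correlation

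*SAP*

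**What the plan says.** **The score.** In SAP Amendment 2, section 7.1.3.3, GM_XXg for each antigen is "the 30 days post last vaccination GMC of Anti" to that antigen in group g. Section 8 defines the calculation: "Calculation of the GMCs will be performed by taking the anti-logarithm in base 10 (anti-log10) of the mean of the log10 concentration/titre transformations". No covariate enters. The four antibody terms each have weight 4 and the four CMI terms weight 1, under a 20th root. Section 7.2.3.3 repeats the GM_XXg definition for the final analysis, but its formula still covers only PD, PE and PilA under a 15th root, so antibody has 12 of 15 weights there. The antibody share is 0.8 in both.

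**The margin.** "Differences of less than 0.02 in terms of summary measures will not be considered sufficient to establish a clear hierarchy between 2 groups".

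**The ANCOVA.** Section 7.1.3.1 (and 7.2.3.1) compares the same two active groups at one month post-Dose 2 on the log10 scale. The model contains group, age category, smoking status, FEV1/FVC "and the pre-Dose 1 concentration (as covariate) as fixed effects". Its named output is the GMC ratio with its 95% CI, and nothing from it feeds the score.

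**CMI.** T-cell frequencies "will be summarised (mean, SD, minimum, Q1, median, Q3, and maximum) by group" (section 7.1.3.2); no model is planned.

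**Allocation.** Protocol 5.2.2.2.1 gives "three study groups in a (1:1:1) ratio (approximately 30 subjects per group") in Step 2, minimised for age, smoking status, centre and FEV1/FVC. Baseline antibody is not among the factors.

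**The concern.** The sponsor chose pre-Dose 1 concentration as a covariate for this very comparison, yet the score that ranks the two formulations leaves it out. Minimisation does not balance baseline antibody. If baseline predicts Day 90 antibody, a chance difference at baseline therefore becomes a difference in the score with nothing to remove it.

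There is also a question of consistency. Section 7.2.3.3 expects a statistically significant GMC difference on at least one antigen to confirm the selected group. That evidence comes from the baseline-adjusted model, while the ranking comes from unadjusted means. The two can point in opposite directions, and the SAP has no rule for that case.

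At stake is which UspA2 content is put forward for later studies.

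**Working it through.** **1. The plan's own anchor.** With x = GM/AvGM, D = 1/(1 + exp(1 - x)). At x = 1, D = 1/2. The weights 4×4 + 4×1 = 20 match the 20th root, so a group whose terms are all average scores 1/2. This agrees with the statement that 1/2 "corresponds exactly at the average level of all subjects in the active groups". The documents give no SD, correlation or precision for the score. The only power-type figure for Step 2 concerns adverse events (78.5% for a 5% event with 30 subjects), and it reproduces: 1 - 0.95^30 = 0.785.

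**2. From GMC ratios to the score.** The slope of D at x = 1 is 1/4. For two equal groups whose GMC ratio on component k is r_k,

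score difference ≈ 0.25 × Σ (w_k/20) × ln r_k.

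A difference of 0.02 therefore means ln r = 0.08, or r = 1.083, if all eight components move together. For anti-UspA2 antibody alone it means ln r = 0.02/(0.25 × 0.2) = 0.4, or r = 1.49. Solving the exact formula gives the same values.

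**3. Effect of a baseline imbalance.** Assume a log10 SD of 0.4 and 30 per group. A 1-SE baseline difference is √(2/30) = 0.258 SD. It shifts the Day 90 log10 difference by ρ × 0.4 × 0.258, where ρ is the baseline to Day 90 correlation. If all four antigens are imbalanced in the same direction and the formulations are identical, the score shift is 0.25 × 0.8 × 2.303 × that amount:

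| ρ | log10 shift | score shift |
|---|---|---|
| 0.3 | 0.031 | 0.014 |
| 0.5 | 0.052 | 0.024 |
| 0.7 | 0.072 | 0.033 |

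For a single antigen the shift is a quarter of this, about 0.004 to 0.008.

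**4. Precision with and without adjustment.** Further assumptions: between-antigen correlation 0.3, CMI log10 SD 0.5, no true difference. The CMI sub-cohort is "approximately the first 15 subjects/group" (Protocol 4.1).

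- Antibody part: 0.2² × (4 + 12×0.3) × 0.4² × 2/30 = 0.003243.
- CMI part: 0.05² × (4 + 12×0.3) × 0.5² × 2/15 = 0.000633.
- SD of the score difference, unadjusted: 0.25 × 2.303 × √0.003876 = 0.0358.
- Chance of a difference of at least 0.02: 2 × [1 - Φ(0.02/0.0358)] = 58%.

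The ANCOVA multiplies the antibody part by F = (1 - ρ²)(1 + 4/53). The second factor is the cost of estimating four covariates with 60 subjects.

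| ρ | F | adjusted SD | ratio to unadjusted | chance of ≥ 0.02 |
|---|---|---|---|---|
| 0 | 1.075 | 0.0370 | 1.03 | 59% |
| 0.3 | 0.979 | 0.0355 | 0.99 | 57% |
| 0.5 | 0.807 | 0.0328 | 0.92 | 54% |
| 0.7 | 0.549 | 0.0283 | 0.79 | 48% |

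Simulations that fitted the full model agree. Over log10 SD 0.3 to 0.5 and between-antigen correlation 0 to 0.6, the ratio was 1.02-1.04, 0.98-0.99, 0.91-0.92 and 0.78-0.81 at these four correlations. At ρ = 0.5 the simulated chance of reaching 0.02 after adjustment was 52% to 55%.

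**5. Break-even.** Setting F = 1 gives ρ² = 4/57, so ρ = 0.26 to 0.27. If minimisation removes the cost of the other three factors, the multiplier is (1 - ρ²)(1 + 1/56), so ρ² = 1/57 and ρ = 0.13.

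**6. Disagreement and wrong choices.** In simulations with no true difference, the raw and adjusted scores favoured opposite groups in 11%, 17% and 22% of trials at ρ = 0.3, 0.5 and 0.7. With a true 1.5-fold anti-UspA2 advantage, a score difference of at least 0.02 in the wrong direction occurred in about 13% of trials unadjusted. With adjustment this fell to about 10% at ρ = 0.5 and 7% at ρ = 0.7, and was essentially unchanged at 0.3.

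**The case against.** The strongest case against the point is that its benefit rests on a correlation the documents do not report. Baseline values below the cut-off are set to half the cut-off (153 EL.U/mL for anti-PD), and many such values could weaken the correlation. Below about 0.13 to 0.27 adjustment gains nothing, and at zero it costs slightly. This stands, and it is why the gain is stated as conditional.

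A reader might infer that enrolled adults must carry natural antibody, so that baseline is bound to be prognostic. The documents do not say so: the protocol's introduction discusses bacterial colonisation and exacerbations, and baseline seropositivity is a result still to be tabulated. The sponsor's own choice of covariate is enough reason to use it consistently.

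Other limits also stand. Three of the four model factors are already minimised, so adjusting for them should remove little. The score only helps selection, subject to safety and CMI profile, in a trial where protocol 10.7 says power and type I error are not controlled. The ANCOVA result already has a confirming role at the final analysis. Section 7.1.3.1 names only the GMC ratio as output, so adjusted group means are not a planned result, although they follow directly from the fitted model.

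These points limit the gain but do not remove it: the score still ranks the formulations, and it does so without the covariate used for the comparison beside it.

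**Conclusion.** The point holds as a low-cost improvement in consistency, with a conditional gain in precision. The mismatch between score and ANCOVA is plain in the text and needs no assumption. Under the stated assumptions, the SD of the score difference changes by about +3% at ρ = 0, -1% at 0.3, -8 to -9% at 0.5 and -21% at 0.7.

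Two stronger readings are not supported. One is that the score is certainly noisier than it needs to be; that requires a baseline correlation above about 0.13 to 0.27, which is unknown here. The other is that adjustment makes the ranking reliable. Even at ρ = 0.7, identical formulations would still differ by at least 0.02 in about 48% of trials (about 33% to 56% over the assumed SDs and between-antigen correlations). The unjustified margin is a separate and larger problem.

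The SDs and correlations are all assumptions. The calculations also take log10 values as normal, ignore censoring at the cut-off, treat the factors other than baseline as non-prognostic, and use the full 30 per group with no ATP exclusions.

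**What to change.** In SAP sections 7.1.3.3 and 7.2.3.3:

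- Define GM_XXg for the antibody terms as the ANCOVA-adjusted Day 90 GMC of group g, from the model in 7.1.3.1 (7.2.3.1) fitted to the two active Step 2 groups.
- State that pre-Dose 1 concentration enters on the log10 scale; the SAP does not give its scale.
- Define AvGM_XX as the adjusted geometric mean over the same two groups, so that 1/2 remains the average, and state the covariate values at which the adjusted means are evaluated.
- Leave the CMI terms unadjusted and keep the fully unadjusted score as a supporting table.
- When editing 7.2.3.3, reconcile its three-antigen formula with the four-antigen formula in 7.1.3.3.

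The cost is SAP wording and a short addition to the output of a model already planned. The downside is a loss of up to about 3-4% in precision if baseline proves not to be prognostic. The 0.02 margin needs its own justification, for example with a bootstrap interval reported for the score difference.

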7.2.3.3. Summary score to support dose selection

The calculation of a summary score for both active groups of Step 2 (i.e. 10-10-10-AS and 10-10-3-AS) will be proposed in order to help the formulation selection. The group(s) with the highest summary score(s) should potentially be the one(s) considered for selection provided it (they) has (ve) an acceptable safety and CMI profile. However note that a difference of less than 0.02 between 2 summary scores will not be sufficient to consider that a formulation should be ranked higher than/preferred to the other.

Unacceptable safety profile encompasses cases such as high occurrence of grade 3 events, occurrence of specific serious adverse event. Unacceptable CMI profile encompasses cases with a pronounced Th₂ response in which there is an isolated elevated IL-13 response, in particular without a response in terms of IFN- γ . The discarding of a group from the selection because of specific safety or CMI reason will be substantiated in the CSR.

If the group(s) ultimately selected for use in upcoming studies for COPD patients is(are) not the one with the highest summary scores at post dose 2 and/or post dose 3, the disqualification of the group(s) with higher summary scores should be adequately justified in the CSR.

The summary scores will be calculated based on the subjects from the ATP cohort.

For each group g , the summary score will summarize how well the group is performing compared to the average active group in terms of the following immunogenicity and CMI results. Before defining the summary score several quantities are introduced (for XX being PD, PE, or PilA):

- GM_{XXg} : the 30 days post last vaccination GMC of Anti- XX of group g
- $AvGM_{XX}$: the 30 days post last vaccination GMC of Anti- XX of all subjects in any active group

Study alias & e-track number(s): NTHI MCAT-001 (201281)

- GM_{CMIXg} : the 30 days post last vaccination GMC of specific Anti-XX CD4+ T cells expressing at least two markers among CD40L, IL-2, TNF-Alpha, IFN-Gamma, IL-13 and IL-17 per million cells of group g
- $AvGM_{CMIX}$ the 30 days post last vaccination GMC of specific Anti-XX CD4+ T cells expressing at least two markers among CD40L, IL-2, TNF-Alpha, IFN-Gamma, IL-13 and IL-17 per million cells of all subjects in any active group

These measures will be transformed in order to be contained between 0 and 1 via the following formulae:

$$D_{XXg} = 1 / (1 + \text{Exp}((AvGM_{XX} - GM_{XXg})/AvGM_{XX}))$$

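### The formulation-selection score is judged against a fixed gap of 0.02, with no measure of sampling error planned for the score or its difference

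*SAP*

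**What the plan says.** Protocol 10.6.3.3 announces a score to support the choice between 10-10-10-AS and 10-10-3-AS, and leaves its calculation and use to the SAP. SAP 7.1.3.3 (Day 90) gives the role of the score: "The group with the highest summary score should potentially be the one considered for selection provided it has an acceptable safety and CMI profile". Choosing a group other than the top scorer has to be justified in the study report.

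The score is a point formula. Each group geometric mean is compared with the pooled active mean ("These measures will be transformed in order to be contained between 0 and 1 via the following formulae"), and the results are then combined: "The summary score for group g will be computed by taking the weighted geometric mean of the several D measures as follows". In 7.1.3.3 this is a 20th root, with weight 4 on each of four antibody terms and weight 1 on each of four CMI terms.

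The margin is stated as "Differences of less than 0.02 in terms of summary measures will not be considered sufficient to establish a clear hierarchy between 2 groups". Section 7.2.3.3 (Day 420) repeats that "a difference of less than 0.02 between 2 summary scores will not be sufficient to consider that a formulation should be ranked higher". That section closes with two further statements absent from 7.1.3.3: the comparisons are exploratory and call for caution, and statistical significance on at least one GMC is expected in support of the selected group.

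Confidence intervals are planned for seropositivity rates, GMCs and single-antigen GMC ratios (SAP 7.1.3.1 and 7.2.3.1). None is planned for the score or the score difference, and 0.02 is not derived anywhere.

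**The concern.** The score makes one formulation the default candidate for later studies in COPD patients, yet it is the one between-group summary reported without any statement of precision. A fixed margin can stand in for an interval only if it is large relative to the sampling error. Here 0.02 looks small for groups of about 30, with CMI terms resting on about 15. If so, the report could present one formulation as ahead when the score gap is within chance variation, and the score itself would give no sign of that.

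**Working it through.** **Inputs from the documents.** Group size: "three study groups in a (1:1:1) ratio (approximately 30 subjects per group" (Protocol 5.2.2.2.1). CMI sub-cohort: "approximately the first 15 subjects/group" (Protocol 4.1). Analysis set: "The summary scores will be calculated based on the subjects from the ATP cohort" (SAP 7.1.3.3). Between-subject SDs and antigen correlations are not given, so ranges are assumed below.

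**The plan's own figures.** The documents state no operating characteristic for the 0.02 rule. The only Step 2 sample-size figure is the chance of seeing an AE of 5% incidence in 30 subjects: 1 − 0.95^30 = 0.785, which agrees with Protocol 10.3. The SAP's reference value also checks: GM = AvGM gives D = 1/(1 + e^0) = 0.5.

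**What a gap of 0.02 means (no SD needed).** With equal group sizes, a GMC ratio R puts the two groups at √R and 1/√R times the pooled mean, so D = 1/(1 + exp(1 − √R)) and D = 1/(1 + exp(1 − 1/√R)).
- All four antibodies, R = 1.105: D = 0.5128 and 0.4878. Scores are 0.5128^0.8 × 0.5^0.2 = 0.5102 and 0.4878^0.8 × 0.5^0.2 = 0.4902. Gap 0.020.
- One antibody, R = 1.5: D = 0.5560 and 0.4543. Scores are 0.5560^0.2 × 0.5^0.8 = 0.5107 and 0.4543^0.2 × 0.5^0.8 = 0.4905. Gap 0.020.
- All eight terms together: R = 1.083.
- Section 7.2.3.3 uses a 15th root without UspA2. Three antibodies together again need R = 1.105 (weight 12/15 = 0.8). One antibody needs about 1.35: D = 0.5404 and 0.4652, and 0.5^(11/15) × (0.5404^(4/15) − 0.4652^(4/15)) = 0.020.

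**Against sampling error.** One standard error of a single-antigen GMC ratio is a factor of 10^(SD × √(2/30)): 1.13, 1.27 and 1.43 at log10 SD 0.2, 0.4 and 0.6.

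**Two identical formulations.** Simulation of the 20th-root score: log10-normal data, equal true means, 30 antibody and 15 CMI subjects per group, correlation 0 to 0.6 among antigens, 20,000 trials per scenario.

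| log10 SD, antibody / CMI | Chance of a gap of 0.02 or more |
|---|---|
| 0.2 / 0.4 | 17% to 42% |
| 0.4 / 0.4 | 43% to 63% (57% at correlation 0.3) |
| 0.6 / 0.6 | 60% to 75% |

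The SD of the score difference runs from 0.014 to 0.063.

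**Sensitivity.**
- A wider grid (SD 0.2/0.3 to 0.6/0.8, correlation 0 to 0.7) gives 14% to 77%. With 27/13 per group, allowing for ATP losses, it gives 16% to 78%. The 15th-root formula with 30/15 gives 20% to 78%.
- At antibody SD 0.10 with CMI SD 0.15 the rate is 0.2% to 9%. At antibody SD 0.10 to 0.15 with CMI SD 0.3 it is 2% to 27%. The low rate therefore needs both SDs to be small.

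**Adding the Day 420 expectation.** Requiring also at least one significant GMC in the same direction (unadjusted t tests in place of the ANCOVA, four-antibody score) gives about 5% to 15% for antibody SD 0.2 to 0.5. At SD 0.4/0.5 and correlation 0.3 the rate falls from 57.6% to 14.6%.

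**When one formulation is truly better.** At SD 0.4/0.4 and correlation 0.3, with a true 2-fold advantage in UspA2 antibody only, the 0.02 rule ranks correctly in about 66% of trials and wrongly in about 6%. Requiring the interval to exclude 0 as well cuts correct ranking to about 16% to 18%.

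**The case against.** Several parts of the defence stand.

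- The SAP says a gap under 0.02 is not enough. A reader might infer that 0.02 or more is declared enough for a clear hierarchy, but the text does not say so.
- A reader might also infer that 0.02 is the only safeguard. It is not: safety and CMI profile can disqualify a group, and the Day 420 section expects a significant GMC.
- Nor would a chance gap pass unseen. GMC ratios with 95% intervals are reported for the same two groups at the same time point, and antibodies carry 16 of the 20 units of weight. A chance gap would often sit beside intervals that include 1.
- The score helps selection and does not dictate it. Protocol 10.7 warns that power and type I error are not controlled.
- If two formulations really are identical in immunogenicity, picking either has no immunological cost. The more relevant risk is ranking the worse one first, about 6% in the case computed above.

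What remains is narrower. The Day 420 sentence is missing from the section that governs the first read-out, and the antigen it refers to is not defined. Neither it nor the single-antigen intervals attaches an error to the composite. A general caution does not tell the reader whether a particular gap is distinguishable from zero.

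**Conclusion.** The point holds as a gap in reporting. The score difference is judged only against a fixed 0.02, which is not derived and carries no measure of precision. That margin corresponds to a GMC ratio of about 1.10 across the antibodies, less than one standard error of a single-antigen ratio even at log10 SD 0.2.

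The figure of 17% to 75% should not be read as the trial's error rate. It rests on SDs and correlations that the documents do not supply, it describes the margin without the Day 420 expectation, and it drops below 10% at antibody SD 0.10 with CMI SD 0.15. The documents do not support a claim that the selection rule is invalid or that selection rests on the score alone. The primary safety objective is unaffected. This is a cheap and worthwhile improvement.

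**What to change.** In SAP 7.1.3.3 and 7.2.3.3:

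1. Report a 95% bootstrap interval for D(10-10-10-AS) minus D(10-10-3-AS). Resample subjects within group, keep CMI sub-cohort membership, and recompute the group means, pooled averages and both scores in each replicate. Use the formula that applies in each section.
2. State that a gap of 0.02 or more whose interval includes 0 will be described as compatible with no difference.
3. Carry the Day 420 caution and the expectation of a significant GMC into 7.1.3.3, and say which antigen or antigens the expectation refers to.

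Do not make an interval that excludes 0 a mandatory condition for preferring a formulation. At this sample size it would sharply reduce the chance of identifying a truly better one, as the 2-fold UspA2 example shows.

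The cost is SAP wording and a short program, with no new data. The downside is that reported rankings will be less clear-cut.
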